Initial assessments will be conducted in the few weeks preceding patients' already-scheduled appointments for dental treatment at TUKSoD. Patients meeting inclusion and exclusion criteria will then be offered I-CBT or the control intervention, to occur immediately prior to their scheduled dental treatment appointment. Efficacy based on primary outcome measures (e.g., reduction from baseline on self-rated and clinician-rated measures of dental anxiety/fear) and secondary outcome measures will be examined at assessments one and three months thereafter. Some additional interview ratings will be gathered from patients after they complete the dental anxiety intervention and after they complete the pursuant dental treatment appointment, and one brief questionnaire will be administered six and twelve months later. Finally, we will examine the impact that the intervention may have on attendance at scheduled dental appointments over the next 12 months.

2) Protocol Title

Efficacy of an Internet-based intervention for dental anxiety

3) Investigators

Page 1 of 28 Revision: May 12, 2023

[name], Associate Professor, Chair, and Residency Director, Pediatric Dentistry and Community Oral Health Sciences, Maurice H. Kornberg School of Dentistry, Temple University

[name], Assistant Professor, Department of Oral Health Sciences, Maurice H. Kornberg School of Dentistry, Temple University

4) Objectives

The primary goal of human subjects activities described in this protocol is to evaluate the efficacy of the Internet-based intervention for dental anxiety among patients presenting to the participating clinic(s). To achieve this overall goal, we propose 3 primary objectives:

Objective 1: We will compare the efficacy of I-CBT as administered by personnel with training and experience in CBT to the efficacy of the intervention as administered by dental assistants who have undergone a brief but specific training in the administration of the intervention, a goal which would allow the greater dissemination of this intervention. We will also examine within-group reduction of anxiety at assessments one and three months after the administration of the intervention.

Objective 2: We will compare the efficacy of the intervention, administered either by CBT personnel or dental staff, to an active control condition, the viewing of the control video and the notification of the dental provider of the patient's score on a measure of dental anxiety before the dental appointment.

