Objective 3: We will examine the impact that the intervention has on attendance at scheduled dental treatment appointments over the next 12 months.

Secondary Objectives:

We will examine whether I-CBT has similar effects on related measures (pain sensitivity, anxiety sensitivity, distress tolerance, symptoms of specific phobia of dental procedures, blood-injury-injection phobia, sleep disturbance and sleep-related impairment, functional impairment due to dental anxiety, and consumer satisfaction) at one- and three-month follow-ups.

We will also examine whether the Internet-based intervention reduces anticipated and perceived pain and anxiety during dental procedures in immediately pursuant appointments for dental treatment.

We will also examine whether baseline levels of distress tolerance and pain sensitivity moderate the efficacy of the dental anxiety intervention.

5) Rationale and Significance

Page 2 of 28 Revision: May 12, 2023

Dental anxiety (i.e., anxiety related to undergoing dental procedures) is a major public health concern, as it leads to underutilization of dental care and poor oral health. Approximately 10-20% of individuals in the US endorse significant dental anxiety, and 10-50% cancel regular dental care appointments or delay treatment for a painful dental condition due to fears of dental procedures (Sohn & Ismail, 2005). Patients with dental anxiety are more likely to be referred for nitrous oxide sedation (Boyle, Newton, & Milgrom, 2009) and use emergency dental services (Kanegane, Penha, Borsatti, & Rocha, 2003), both of which increase individual and public dental healthcare costs. Dental anxiety has been consistently associated with increased oral health problems and impairment (e.g., more cavities; Armfield, Stewart, & Spencer, 2007). Few studies have examined the efficacy of psychological treatments for dental anxiety (Gordon, [name], Tellez, & Ismail, 2013), and most of the existing empirically supported psychological interventions cannot be easily disseminated within dental healthcare settings, as they must be administered by highly trained clinicians over a number of sessions. Therefore, it is the goal of our ongoing research program to develop a brief online therapy for dental anxiety that could be easily implemented in dental clinics, allowing for broader dissemination.

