Pain Intensity Numeric Rating Scale (PI-NRS). The PI-NRS is a widely utilized 11-point measure that assesses physical pain intensity on a scale ranging from 0 (no pain) to 10 (worst possible pain). The PI-NRS has been used to assess pain intensity in several studies conducted in medical settings (Farrar et al., 2001, 2010; Rowbotham et al., 2004; van der Roer, 2006). Anxiety increases subjective pain experience, and therefore this scale will be used to assess the intensity of dental related pain that participants experienced during their scheduled dental appointment and expect to experience at their next dental appointment. The PI-NRS will be administered as part of the post-dental-appointment debriefing interview.

Attendance at Dental Appointments

Given that avoidance of dental appointments is strongly connected to dental anxiety, we will also assess whether the Internet-based dental anxiety intervention increases attendance at future dental appointments. We will utilize TUKSoD's automated scheduling system (axiUm, http://www.axiumdental.com/) to do so. It is acknowledged that attendance may be influenced by factors unrelated to dental anxiety, but it is a reasonable hypothesis that anxious avoidance plays a role in attendance, and individuals with dental phobia are less likely to visit a dentist at least once a year than persons without. Thus, it is of interest to determine whether attendance at appointments scheduled prospectively after the index appointment is affected by treatment, and we will monitor this for the following 12-month interval. These data will not be collected for active control patients, who will be offered the intervention to be administered before their first scheduled dental appointment after the completion of the 3-month follow-up.

Planned Analyses

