injury-injection phobia). Statistical significance will be set at p < .05. MI will be used to handle missing follow-up data as described below.

Specific Aim 3

Aim 3 examines the impact of the intervention on attendance at scheduled dental appointments over the following 12-month period to determine whether the intervention affects avoidance of dental procedures. First, we will examine whether the overall attendance rate is changed from pre- to post-intervention using a one-sample Chisquare test comparing the 12-month periods immediately before and immediately after the delivery of the intervention. The two intervention groups combined will be used for this analysis. We will also use a Chi-square test to compare post-intervention attendance rates between the two intervention groups. We expect the attendance rates will be similar for the two groups. Finally, we will conduct logistic regression analyses predicting attendance/nonattendance among intervention patients who did or did not demonstrate reduction in dental anxiety at 3-month follow-up. Relevant demographic characteristics and other potential confounding variables or moderators will be included in the final logistic models.

Missing Data

MI will be used to handle missing follow-up data when conducting ITT analysis for Specific Aims 1 and 2. There will be three steps in the MI procedure: 1) The missing follow-up data will be filled in 100 times to generate 100 complete datasets; 2) The 100 datasets will be analyzed by analyses of covariance with follow up scores at 1-month or 3-month as outcomes and treatment groups as the independent variable (Tr1 vs. Tr2 for Specific Aim 1, or Tr1 + Tr2 vs. AC for Specific Aim 2), controlling for baseline scores; 3) The results from the 100 complete datasets will be combined for the MI inference (Rubin 1987). SAS PROC MI and PROC MIANALYZE will be used for multiple imputation analysis using SAS 9.4 (SAS Institute Inc., Cary, NC, USA).

Analysis of Secondary Objectives

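### Aim 3 asks what effect I-CBT has on attendance, but control attendance is not collected and no planned analysis compares I-CBT with control

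*Combined protocol and SAP*

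**What the plan says.** Section 4 (Objectives) introduces its list with "To achieve this overall goal, we propose 3 primary objectives". The third reads: "We will examine the impact that the intervention has on attendance at scheduled dental treatment appointments over the next 12 months".

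Section 8(c), Attendance at Dental Appointments, makes the question directional: "we will also assess whether the Internet-based dental anxiety intervention increases attendance at future dental appointments". It adds that the interest lies in "whether attendance at appointments scheduled prospectively after the index appointment is affected by treatment". It accepts that factors other than dental anxiety may influence attendance. On the control arm it states: "These data will not be collected for active control patients". The reason given is that controls will be offered the intervention before their first dental appointment after the 3-month follow-up.

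Section 8(c), Specific Aim 3, gives its purpose as "to determine whether the intervention affects avoidance of dental procedures" and lists three analyses:

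1. A before-after comparison with both I-CBT arms pooled, "using a one-sample Chisquare test comparing the 12-month periods immediately before and immediately after the delivery of the intervention".
2. A chi-square test between the two I-CBT arms, with the remark "We expect the attendance rates will be similar for the two groups".
3. Logistic regression of attendance among I-CBT patients according to whether their anxiety had fallen at 3 months. Demographic variables and other potential confounders enter the final models.

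Planned Analyses names MDAS and the ADIS-5 fear rating as the primary outcomes. Attendance is not among them.

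**The concern.** The objective, the attendance section and the stated purpose of Aim 3 are all causal: they ask what the intervention does to attendance. The trial has a randomised control arm that could speak to this, but the attendance data are restricted to patients who received I-CBT. Without a concurrent comparator, a rise in attendance could be reported under a primary objective as an effect of I-CBT although no planned comparison supports that attribution.

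There is a second, smaller problem of method. A one-sample chi-square takes its reference rate as a known constant. Here the reference is the same patients' own earlier attendance, which is estimated and paired with the later rate.

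**Working it through.** **What each analysis can show**

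| Aim 3 analysis | Comparison | What it leaves unresolved |
|---|---|---|
| Pooled before-after | I-CBT patients with themselves | Time trend, and notification of the provider, which the Abstract says happens for all participants |
| Between I-CBT arms | Psychology staff with dental assistants | Randomised, but both arms receive I-CBT; similar rates fit equal benefit or no benefit |
| Responder regression | I-CBT patients whose anxiety fell with those whose anxiety did not | Groups form after randomisation, and the predictor is measured 3 months into the 12-month outcome window; covariates do not restore randomisation |

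No other section adds a control comparison of attendance.

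**How easily an unrelated rise would reach significance**

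The plan gives no attendance rate, effect size or power for Aim 3, so there is no figure to reproduce. What follows is an illustration.

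- From Recruitment Methods: about 550 patients in three roughly equal arms, so 550 × 2/3 ≈ 367 on I-CBT and 550/3 ≈ 183 controls.
- Assumed: one yes/no outcome per patient, prior attendance p of 60% or 70%, pre/post correlation r from 0 to 0.5, and two-sided 5%. The plan states 5% for Aims 1 and 2 but gives no level for Aim 3.

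Let the later rate be q = p + s, where s is a rise not caused by I-CBT. Then:

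- p11 = pq + r√[p(1−p)q(1−q)]
- discordant share D = p + q − 2·p11
- P(significant) ≈ Φ{[s − 1.96√(D/n)] / √[(D − s²)/n]}, the opposite tail being negligible

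Example with n = 367, p = 0.70, s = 0.05, r = 0.3: p11 = 0.525 + 0.3 × 0.1984 = 0.5845. D = 0.281, √(D/n) = 0.0277 and √[(D − s²)/n] = 0.0275. The result is Φ[(0.05 − 0.0542)/0.0275] ≈ 44%.

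| n = 367 | r = 0 | r = 0.3 | r = 0.5 |
|---|---|---|---|
| p = 60%, 5-point rise | 28.7% | 38.5% | 50.4% |
| p = 70%, 5-point rise | 32.8% | 43.9% | 56.9% |
| p = 60%, 8-point rise | 61.5% | 76.7% | 88.8% |
| p = 70%, 8-point rise | 69.3% | 83.6% | 93.4% |

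If only 184 patients contribute, the ranges are 17-33% for 5 points and 36-69% for 8 points.

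**The one-sample test**

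With the patient as unit and no true change, the variance of the before-after difference is 2(1 − r) times the variance that a one-sample test assumes. The factor exceeds 1 when r is below 0.5 and is less than 1 when r is above 0.5. The actual error rate may therefore be too high or too low, and the documents do not determine which. A paired test avoids the problem.

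**What a 12-week control comparison could detect**

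Solve Φ[(d − 1.96·SE_pooled)/SE_unpooled] = 0.80 for the difference d:

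| Share with an outcome | I-CBT vs control | Control 60% | Control 70% |
|---|---|---|---|
| All | 367 vs 183 | 11.9 points | 10.8 points |
| 80% | 294 vs 146 | 13.2 | 11.9 |
| Half | 184 vs 92 | 16.4 | 14.7 |
| 30% | 110 vs 55 | 20.6 | 18.2 |

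**The case against.** The protocol is open about the limitation. It says controls are left out, gives the reason, and admits that attendance has other causes. Attendance is not a named primary outcome. The later offer of I-CBT does rule out an uncontaminated 12-month comparison with untreated controls. All of this stands, and it makes the point mainly one of claim and label. It does not turn an uncontrolled comparison into evidence of impact, and it does not explain omitting the period before controls are offered I-CBT.

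The illustration can also be called circular, since it assumes a rise and then reports how often that rise would be detected. That is fair. It is not evidence that attendance will drift; it shows only that a modest drift would often look like a finding.

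A reader might infer more than the documents support:

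- **That Objective 3 itself asks for an increase.** It asks for impact; only the attendance section speaks of an increase.
- **That withdrawing patients who miss the index visit and do not rebook within 72 hours manufactures a rise.** Suppose each patient has a stable attendance propensity π. Selecting on index attendance then moves the expected rate to E[π²]/E[π] in both periods, which raises the level but not the difference. A rise would follow if the earlier period used different patients, if the index visit were counted, or if index attendance tracked the later period more closely than the earlier one.
- **That the attended index visit inflates the later rate.** Aim 3 starts the later period at delivery of the intervention, but the attendance section counts only appointments after the index visit. The two need aligning; the literal reading of Aim 3 should not be taken as the plan.
- **That the one-sample test inflates false positives.** The direction depends on an unknown correlation.

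**Conclusion.** The concern holds in this form: the attendance question is worded causally under a primary objective, control attendance is not collected, and none of the three Aim 3 analyses can attribute a change to I-CBT. The one-sample chi-square also does not suit paired data. Both should be fixed before the Aim 3 analysis.

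The non-attribution rests on the text alone. The size is illustrative: 29-57% for a 5-point unrelated rise and 62-93% for an 8-point rise in 367 patients, under assumed rates and correlations and a correct paired test. The primary MDAS and ADIS-5 fear analyses of Aims 1 and 2 are not affected.

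**What to change.** 1. **Wording.** State in Objective 3, the attendance section and Aim 3 that the 12-month before-after and responder analyses are uncontrolled and are not evidence of an I-CBT effect. Keep the between-arm test, described as a comparison of who delivers I-CBT.
2. **Before-after method.** Replace the one-sample chi-square with McNemar's test (patient as unit) or GEE (appointment as unit). Name the unit, say how patients with no scheduled appointment count, use the same patients in both periods, and start the later period after the index visit so that Aim 3 agrees with the attendance section.
3. **Responder analysis.** Count only appointments after the 3-month follow-up.
4. **Optional, if consent and the IRB allow.** Extract scheduling-system attendance for controls. Compare pooled I-CBT with control by randomised arm over the 12 weeks after the index appointment or its scheduled date, before controls are offered I-CBT. Include all patients who signed consent at the clinic visit; the arm is not revealed before then. Keep withdrawn patients where their data may be used, because the missed-appointment rule is worded around the I-CBT session and its application to controls is unclear. Report by arm how many had no appointment in the window.

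Cost: item 1 is wording. Items 2 and 3 are small analysis changes. Item 4 needs an extract for about 183 controls and any withdrawn I-CBT patients, linkage before the name-code file is destroyed at study end, and IRB confirmation. The timeline targets completion by July 31, 2023, which is 19 + 30 + 31 = 80 days after the May 12, 2023 revision. Item 4 covers 12 of 52 weeks (23%) and detects differences of about 11-21 points under the assumed rates. Controls who know of the later offer might also defer appointments. The 12-month question stays descriptive either way.

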We propose general statistical analyses and sample size considerations for the U01 trial. Initial analyses will be conducted to determine normality of distributions of the continuous variables, and any necessary transformations will be conducted. Primary outcomes will be the MDAS (score ranging from 5 to 25) and the rating of fear of dental procedures from the ADIS-5 (0=no fear to 8=very severe fear). All eligible patients will be randomly assigned to one of the three conditions described above. Although randomization should provide relatively comparable groups, demographic variables that differ between groups and are correlated with the primary outcomes will be used as covariates. Patients will receive a full battery assessment of outcome measures at baseline and 1 and 3 months after the day of their index dental appointment (as well as assessments on the day of their index dental appointment).

Page 16 of 28 Revision: May 12, 2023

Preliminary statistical analysis will include measures of central tendency and dispersion, as well as an examination of the bivariate relationships among the primary and secondary outcome variables (e.g., client satisfaction, blood-injury-injection phobia), potential moderators (e.g., distress tolerance and pain sensitivity), and demographic characteristics.

Differences between the groups on baseline demographic, clinical and psychological measures will be examined using χ^2 (Pearson) or Student's *t*-tests, as appropriate. Moreover, differences on the variables listed above among completers and drop-outs will also be explored. Both per protocol and intention to treat (ITT) analyses will then be conducted.

Specific Aim 1

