Aim 1 will test the equivalence hypothesis (Ho: the two intervention conditions are not equivalent). MDAS and ADIS fear scores will be the primary outcomes to be compared between two intervention conditions for equivalence. The two one-sided tests (TOST) procedure of Schuirmann (1987) will be used to conduct the equivalence test. Linear mixed-effects models for repeated measures will be used to assess differences between intervention groups using the MDAS and ADIS fear rating as continuous outcome variables. Linear mixed-effects models will also investigate the treatment effect on dental anxiety or fear after accounting for other confounding factors. Similar analyses will be conducted for secondary outcome measures (pain sensitivity index, anxiety sensitivity index, sleep disturbance and sleep-related impairment scales, disability scale, distress tolerance scale, client satisfaction and blood-injury-injection phobia). Statistical significance will be set at p < 0.05. Multiple imputation (MI) will be used to handle missing follow-up data as described below.

Aim 1 will also determine whether the Internet-based intervention reduces dental anxiety/fear as determined by self-ratings or assessor ratings at one month and three months post-intervention. Initially, we will assess within-group change of anxiety or fear scores for each condition separately using paired *t*-tests. Linear mixed-effects models will be used to estimate within-group reduction of anxiety/fear at assessments one and three months after the administration of the intervention adjusting for other covariates.

Specific Aim 2

Aim 2 will assess the superiority hypothesis (Ho: there are no significant differences between the interventions and control). MDAS and ADIS-5 fear scores will be the primary outcomes to be compared. Initially, we will assess the differences between the interventions and control using two-sample *t*-tests. The main analysis will be based on linear mixed-effects models for repeated measures (using the MDAS score and ADIS-5 fear rating as continuous outcome variables) to assess differences between intervention and control groups. Linear mixed models will also investigate the treatment effect on dental anxiety or fear after accounting for other confounding factors. Similar analyses will be conducted for secondary outcome measures (e.g., client satisfaction and blood-

Page 17 of 28 Revision: May 12, 2023

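### Demographic covariates are selected from the trial data and the main mixed model does not say how baseline is handled; a short list fixed in advance settles both

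*Combined protocol and SAP*

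**What the plan says.** Four places in section 8c of the combined protocol and SAP bear on covariates for Aims 1 and 2.

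- **Planned Analyses, selection rule:** "demographic variables that differ between groups and are correlated with the primary outcomes will be used as covariates". No candidate list, test threshold or correlation cut-off follows.
- **Planned Analyses, baseline testing:** "Differences between the groups on baseline demographic, clinical and psychological measures will be examined using" chi-square or t-tests.
- **Specific Aims 1 and 2:** for Aim 2, "The main analysis will be based on linear mixed-effects models for repeated measures", and "Linear mixed models will also investigate the treatment effect on dental anxiety or fear after accounting for other confounding factors". Aim 1 has a parallel sentence, and its within-group models are fitted "adjusting for other covariates". The confounders and covariates are not named. The fixed effects are not listed, and the text does not say whether the baseline score is a covariate or one of the repeated responses.
- **Missing Data:** for the ITT analysis of Aims 1 and 2, the 100 imputed datasets are "analyzed by analyses of covariance with follow up scores at 1-month or 3-month as outcomes and treatment groups as the independent variable", "controlling for baseline scores". Here baseline is fixed in advance, with no imbalance condition.

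**The concern.** In a randomised trial, a baseline difference between arms is chance by construction. Testing for it says nothing about which variables predict the outcome, and prognosis is what makes a covariate worth having. A rule that requires both imbalance and correlation will usually discard a prognostic variable because the arms happened to balance on it. It also means that the adjusted model cannot be written down before the data are examined. The unnamed confounders leave further room for choice.

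Baseline is a separate gap. The selection rule covers demographic variables only, so it does not settle how the baseline MDAS or ADIS-5 fear score enters the mixed model. The plan therefore has two between-arm models for the same contrasts. One is explicit about baseline, the other is silent, and nothing reconciles them. At stake are the width of the intervals for the equivalence and superiority contrasts, and whether the primary estimate can be shown to have been specified in advance.

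**Working it through.** **Inputs from the document.** N = 550 in three roughly equal arms (Abstract; Recruitment Methods), so 550/3 ≈ 183 per arm, and about 367 vs 183 when Aim 2 pools the I-CBT arms. Alpha is 0.05 (Specific Aims 1 and 2). MDAS test-retest r is 0.82 (Initial Screening Measures), taken as an upper bound for the baseline/follow-up correlation. No power, effect size, SD or equivalence margin accompanies the 550, so there is no plan figure to reproduce.

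**Assumptions.** Baseline/follow-up correlation r of 0.4 to 0.7. Demographic R² of 1% to 10%, as a share of the variance left after baseline. Effect sizes, margin and number of candidates as stated below.

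**Step 1: how often the rule adds anything.** The chance that at least one of k independent candidates differs at p < 0.05 is 1 − 0.95^k: 14% for k = 3, 23% for k = 5, 34% for k = 8. The rule also requires correlation with the outcome. In 4,000 simulated trials per setting (183 vs 367, five candidates, both tests at p < 0.05, R² 5% or 10%, r 0.5 or 0.82), any covariate was selected in 6% to 19% of trials.

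**Step 2: what the rule costs when baseline is in the model.** The SE without the demographics, relative to the SE with them, is 1/√(1 − R²). For Aim 2, power ≈ Φ(d/SE − 1.96), with SE = √(1 − R²) × √(1/183 + 1/366) in residual SD units. At an assumed d = 0.25 and R² = 0, SE = 0.0905 and power = Φ(2.76 − 1.96) = 0.789.

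| R² | SE ratio | Aim 2 power with demographics | Gain over none |
|---|---|---|---|
| 1% | 1.005 | – | – |
| 2% | 1.010 | 0.797 | 0.8 points |
| 5% | 1.026 | 0.809 | 2.0 points |
| 10% | 1.054 | 0.829 | 4.0 points |

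The last column compares with no demographics at all. In simulation against the rule itself (r = 0.5, R² 10%, d = 0.22), power was 0.807 with baseline plus the rule and 0.833 with baseline plus all five, a gap of 2.6 points. In the corresponding null runs, the empirical SD of the estimate was 0.0783 with baseline only, 0.0775 with baseline plus the rule, and 0.0752 with baseline plus all five, so the rule recovers little of the available gain. Type I error under the rule was 0.047 to 0.053.

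For the Aim 1 equivalence test (183 vs 183, one-sided 0.05, assumed margin 0.30 residual SD, true difference zero), power is 0.779 without demographics and 0.790, 0.806 and 0.832 at R² of 2%, 5% and 10%.

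**Step 3: what the handling of baseline is worth.** At one follow-up time, with equal SDs at baseline and follow-up, the variances are proportional to 1 for a follow-up-only contrast, 2(1 − r) for change, and 1 − r² for ANCOVA. The SE relative to ANCOVA is therefore 1/√(1 − r²) for follow-up only and √(2/(1 + r)) for change.

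| r | Follow-up only | Change |
|---|---|---|
| 0.4 | 1.09 | 1.20 |
| 0.5 | 1.15 | 1.15 |
| 0.6 | 1.25 | 1.12 |
| 0.7 | 1.40 | 1.08 |

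This gives 9% to 40% for follow-up only and 8% to 20% for change. A mixed model with baseline as a response and baseline means constrained equal across arms would recover most of this.

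**The case against.** The best defence is that the selection rule is not the only way into a model. A reader might infer from it that covariates enter only when the arms happen to differ. The document does not support that. The ANCOVA under Missing Data always includes baseline, the mixed models adjust for other factors with no imbalance condition, and the Aim 3 logistic models include demographics without one. The largest likely gain in precision is therefore kept in the imputed-data analysis.

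Three other strong readings also fail.

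- **A large power loss.** With four independent demographics correlated 0.2 or 0.3 with the outcome and no baseline score, simulated power is 78% vs 84%, or 80% vs 93%. Those inputs imply R² of 4 × 0.2² = 16% and 4 × 0.3² = 36%. Nothing in the document supports them, and they omit a covariate that the ANCOVA includes.
- **Baseline is excluded from the mixed model.** Silence is not exclusion. Outcomes are measured at baseline, 1 and 3 months, and mixed models are used for within-group reduction, which fits baseline being a response. What stands is that its handling is unstated.
- **Inflated type I error.** A mechanical rule showed none. If an analyst were free to report the most favourable subset of unnamed covariates, simulated error reached about 6% to 10% on assumed R² of 5% to 16%. That is a worst case which the text does not rule out, not something it plans.

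It is also fair to say that the rule does not specify whether the correlation is with baseline or follow-up scores, so the follow-up outcome may not be consulted. Even so, the model would still depend on data seen after randomisation.

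**Conclusion.** The point stands as a modest but real fault of specification. Demographic covariates are chosen by observed imbalance and correlation, further confounders are unnamed, and the mixed model's treatment of baseline is neither stated nor reconciled with the ANCOVA.

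With baseline adjusted, the demographic rule costs about 0.5% to 5% in SE for assumed R² of 1% to 10%. Aim 2 power falls by about 1 to 3 points in simulation, or up to 4 by the formula at R² 10%. The baseline question is larger: 9% to 40% in SE for a follow-up-only contrast and 8% to 20% for a change contrast, relative to ANCOVA at assumed r of 0.4 to 0.7, if the mixed model turned out to be either of those. All of these sizes rest on assumed correlations, R² and effects, since the document gives none. No type I inflation is claimed for the rule as written. The reason to act is that the remedy is nearly free and makes the primary model fixed in advance.

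**What to change.** Replace the selection sentence under Planned Analyses with a short covariate list, fixed before any outcome comparison by arm. For the between-arm models of Aims 1 and 2, the list should contain:

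- the baseline score of the outcome being analysed, either as a covariate or as a response with baseline means constrained equal across arms, stating which;
- a few named demographics already collected, such as age, which is asked at screening;
- recruiting clinic, if the Graduate Clinics are opened and more than one clinic enrols.

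Use the same list in the mixed model and in the ANCOVA under Missing Data, whatever imbalance is observed. Replace the references to other confounding factors in the between-arm models with this list, or label any further adjustment as a sensitivity analysis. Baseline comparisons may stay as description, but their significance tests should not select covariates. The within-group reduction models, where baseline is a response, are not affected.

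The cost is one or two sentences and a few degrees of freedom out of about 550. No new data are needed.
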